7.7.1.1. Anti-malarials

Anti-malarial therapies for SLE may be continued or dose adjusted during the study, and will be allowed within the definitions of the efficacy endpoints. A new anti-malarial (e.g., hydroxychloroquine, chloroquine, quinacrine) may not be started during the course of the study for SLE. Starting any new anti-malarial treatment for SLE after Day 1 will declare the participant a treatment failure.

For non-SLE reasons (e.g., for the experimental treatment of COVID-19) an anti-malarial may be initiated for a subject not previously on an anti-malarial, or dose increased above the common allowable maximum doses (defined below) according to the following guidelines, for short-term treatment:

- < 21 days treatment duration
- Not during the intervals within 8 weeks before the key efficacy visits (actual visit date) at Weeks 52, 64, and 104.

An anti-malarial may be replaced by another anti-malarial due to documented toxicity or lack of availability at any time during the study.

The common allowable maximum doses of anti-malarial drugs are:

- Hydroxychloroquine 400 mg/day
- Chloroquine 500 mg/day
- Quinacrine 100 mg/day

For compounded anti-malarials, no individual component may exceed the maximum dose above.

Clinical loading dose is permitted for initiation or replacement.

NOTE: The use of anti-malarials for anti-malarial prophylaxis is permitted.

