7.7.1.5. Nonsteroidal Anti-inflammatory Drugs (NSAIDs), Aspirin, and Acetaminophen

Since NSAIDs and aspirin may affect efficacy parameters (e.g., arthritis) and may affect renal function (NSAID nephropathy), the use of these agents should be initiated and stabilized prior to entry into the trial.

NSAIDs may be continued and dose adjusted as clinically indicated until 8 weeks before efficacy visits, i.e., Weeks 52, 64, and 104. During the intervals of 8 weeks before these efficacy endpoints, any increase in the NSAID dose above the dose at Day 1 or the visit day starting the interval of 8 weeks prior to these key efficacy visits, whichever is higher, will declare the participant as a treatment failure unless the NSAID is given for <7 days. The day of the Week 44, 56, and 96 visits will count as the start of these 3 intervals.

New NSAIDs may not be added after Day 1 unless given for <7 days. Initiation of an NSAID after Day 1 that is given \ge 7 days will declare the participant as a treatment failure.

An NSAID may be replaced with another NSAID due to documented toxicity or lack of availability.

Daily doses of aspirin up to 1000 mg/day are allowed at any time during the study. Daily doses of aspirin above 1000 mg/day may be initiated at any time up to the Week 44 visit and may continue through the end of the study. For participants who never received an aspirin regimen at a dose >1000 mg/day between the Day 1 and Week 44 visit, starting a new aspirin regimen at a dose >1000 mg/day after the Week 44 visit will declare the participant a treatment failure unless the aspirin is given for <7 days.

Acetaminophen (paracetamol) is primarily an analgesic and lacks the anti-inflammatory properties of other NSAIDs. The use of acetaminophen is recommended when possible to treat non-SLE related conditions, in the absence of a pre-existing hepatic function deficiency.

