15.6.15.3. General Conventions

- Assessment of dose is based on analysis dose. Analysis dose is daily dose adjusted for dosing frequency, and in the case of steroid is converted to prednisone equivalents. Exception is intra-articular dose where analysis dose is not populated.
- In the event there are multiple visit dates within a visit window, the date for determining treatment failure, will be the earliest date at which efficacy data (from SLEDAI-2K (IBA), SLEDAI-2K (PI), PGA, and SLE Flare) is recorded. This may be different than the earliest visit within that window.
- If a critical visit (Week 52, 64 , and 104], is missing from efficacy data (from SLEDAI-2K (IBA and PI), PGA, SLE Flare, LLDAS) then the date is imputed as the target day for that visit.
- Actual visit date, not target visit date, is used to assess treatment failures.
 - If the subject’s Day 169 (Week 24) study visit occurs on Day 171, the date for Day 171 is used when applying the treatment failure rules.
- Prohibited medications/dosages started on the date of early withdrawal are considered a TF (see clarification below for steroids). If the prohibited medication/dose starts after the date of withdrawal it will not be part of the TF assessment.

- All potential TF rule violation are output programmatically and all adjudicated.
- Clinical may amend the date of TF during adjudication if, for instance, a subject did not meet the criterion on the date identified by the program but did meet it later.

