15.6.15.5. Anti-malarials

Dose of anti-malarial at baseline is the dose the subject received on the treatment start date (Day 1). If a patient is receiving an anti-malarial at baseline it will be assumed that the dose is stable and not a loading dose.

Anti-malarial therapies may be continued, or dose adjusted during the study.

For non-SLE reasons (e.g., for the experimental treatment of COVID-19) an anti-malarial may be initiated for a subject not previously on an anti-malarial, or dose increased above

the common allowable maximum doses (defined below) according to the following guidelines, for short-term treatment:

- < 21 days treatment duration
- Not during the intervals within 8 weeks before the key efficacy visits (actual visit date) at Weeks 52, 64, and 104.

An anti-malarial may be replaced by another anti-malarial due to documented toxicity or lack of availability at any time during the study.

Clinical loading dose is permitted for initiation or replacement. Whether or not the dose was a loading dose will be assessed by clinical adjudication.

The common allowable maximum doses of anti-malarial drugs are:

- Hydroxychloroquine – 400 mg/day
- Chloroquine – 500 mg/day
- Quinacrine – 100 mg/day

For compounded anti-malarials, no individual component may exceed the maximum dose above.

NOTE: The use of anti-malarials for anti-malarial prophylaxis is permitted.

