15.6.15.6. Other Immunosuppressant Agents

Arms A, B, and C

- Starting any new immunosuppressant agent after Day 1 for increased lupus disease activity will cause the participant to be declared a treatment failure. An immunosuppressant agent may however be replaced with one of the agents listed below due to documented toxicity or lack of availability. Replacement to be determined by clinical review
- New topical immunosuppressive agents (e.g., eye drops, topical creams) are allowed after Day 1.

Arms A and B

- Participants can maintain their baseline stable immunosuppressant regimen or adjust their dose as clinically required, up to the Week 4.
- At or prior to the Week 4 visit, immunosuppressants will be discontinued.
- All immunosuppressant medications post Week 4 (day after the visit 4 visit date) will be clinically reviewed to determine if they are a treatment failure.

Arms C

- Participants may continue their baseline immunosuppressant agents throughout the study.
- Dosage of existing immunosuppressant agents may be increased as clinically necessary until Week 12. From the day after the Week 12 visit, any increase in dose over the baseline (Day 1) or Week 12 visit dose, whichever is higher, will cause the participant to be declared a treatment failure.

The common allowable maximum doses for immunosuppressant agents at baseline (Day 1) and during the study (pre Week 4 for Arms A and B) are listed below:

- Azathioprine – 300 mg/day
- 6-mercaptopurine – 300 mg/day
- Mycophenolate mofetil (PO)/ mycophenolate mofetil hydrochloride (IV) – 4 g/day
- Mycophenolate sodium (PO) – 2.88 g/day
- Methotrexate – 25 mg/week
- Oral cyclophosphamide – 2.5 mg/kg/day
- Cyclosporine – 4 mg/kg/day*
- Tacrolimus – 0.2 mg/kg/day*
- Sirolimus – 2 mg/day*
- Thalidomide – 200 mg/day
- Leflunomide – 40 mg/day*
- Mizoribine – 150 mg/day
- Other immunosuppressant agents not listed above, the investigator must contact the Medical Monitor for approval

*Clinical loading dose is permitted when replacing immunosuppressant agents.

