15.6.15.7. Nonsteroidal Anti-inflammatory Drugs (NSAIDs), Aspirin, and Acetaminophen

NSAIDs and aspirin should be initiated and stabilized prior to entry into the trial.

Baseline is defined as the NSAID/Aspirin received on the treatment start date (Day 1)

NSAIDs may be continued and dose adjusted as clinically indicated until 8 weeks before efficacy visits, i.e., Weeks 52, 64, and 104. During the intervals of 8 weeks before these efficacy endpoints, any increase in the NSAID dose above the dose at Day 1 or the visit day starting the interval of 8 weeks prior to these key efficacy visits, whichever is higher, will declare the participant as a treatment failure unless the NSAID is given for <7 days. The day of the Week 44, 56, and 96 visits will count as the start of these 3 intervals.

An NSAID may be replaced with another NSAID due to documented toxicity or lack of availability. Replacement due to toxicity/ lack of availability will be assessed during clinical adjudication.

New NSAIDs may not be added after Day 1 unless given for <7 days. Initiation of an NSAID after Day 1 that is given ≥ 7 days will declare the participant as a treatment failure.

NSAIDs with an administration route of ‘TOPICAL’ or ‘CONJUNCTIVAL’ will not be considered as TF’s.

Aspirin will not be considered in the NSAID TF rules.

Daily doses of aspirin up to 1000 mg/day are allowed at any time during the study. Daily doses of aspirin above 1000 mg/day may be initiated at any time up to the Week 44 visit and may continue through the end of the study. For participants who never received an aspirin regimen at a dose >1000 mg/day between the Day 1 and Week 44 visit, starting a new aspirin regimen at a dose >1000 mg/day after the Week 44 visit will declare the participant a treatment failure unless the aspirin is given for <7 days.

Daily doses of aspirin above 1000 mg/day may not be initiated in the 8 weeks before Week 64 and 104. The same rules as at Week 44 will be applied at Weeks 56 and 96

ACETYLSALICYLATE LYSINE (in mg) will be converted to standardised dose by multiplying by 0.556.

Acetaminophen (paracetamol) is primarily an analgesic and lacks the anti-inflammatory properties of other NSAIDs. The use of acetaminophen is recommended when possible to treat non-SLE related conditions, in the absence of a pre-existing hepatic function deficiency.

PRN use of NSAIDs or Aspirin will be identified as a potential TF and reviewed on a by subject review basis.

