15.7.2.1. Missing and Partial Dates

| Element | Reporting Detail |
|---|--|
| General | 
 • Partial dates will be displayed as captured in subject listing displays. |
| Adverse Events | 
 • The eCRF allows for the possibility of partial dates (i.e., only month and year) to be recorded for AE start and end dates; that is, the day of the month may be missing. In such a case, the following conventions will be applied for calculating the time to onset and the duration of the event: 
 ○ Missing Start Day: First of the month will be used unless this is before the start date of study treatment; in this case the study treatment start date will be used and hence the event is considered On treatment as per Appendix 4: Study Phases and Treatment Emergent Adverse Events. ○ Missing Stop Day: Last day of the month will be used, unless this is after the stop date of study treatment; in this case the study treatment stop date will be used. • Completely missing start or end dates will remain missing, with no imputation applied. Consequently, time to onset and duration of such events will be missing. |
| Concomitant Medications/ Medical History | 
Missing concomitant medication start date (CMSTDT) is imputed as treatment start date (TRTSDT) unless:
 
 ○ concomitant medication end date (CMENDT) is prior to treatment start date (TRTSDT), whether CMENDT is complete (DD/MM/YY) or partial (some combination of CMENDT day, month or year imputed) OR ○ The month or month and year of the partial CMSTDT are different from the month and/or year of TRTSDT OR |

| Element | Reporting Detail |
|---------|--|
| | 
○ "Taken prior to study?" is checked. 
If any of the above conditions are met then CMSTDT is imputed with JAN for missing month and 01 for missing day, whatever is applicable. The recorded partial date will be displayed in listings.
 |

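### Restricted drugs with an unknown start date are dated to Day 1, so some true on-study starts escape the treatment-failure rules and their adjudication

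*SAP*

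**What the plan says.** The default for concomitant medications is in SAP 15.7.2.1: "Missing concomitant medication start date (CMSTDT) is imputed as treatment start date (TRTSDT) unless" one of three exceptions applies. Two of these are an end date before first dose and a ticked box for use before the study. The third is a mismatched partial date: "The month or month and year of the partial CMSTDT are different from the month and/or year of TRTSDT OR". When an exception applies, a missing month becomes January and a missing day becomes the first.

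The new-drug failure rules turn on Day 1:

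- Anti-malarials (Protocol 7.7.1.1): "Starting any new anti-malarial treatment for SLE after Day 1 will declare the participant a treatment failure".
- Immunosuppressants, all arms (SAP 15.6.15.6): "Starting any new immunosuppressant agent after Day 1 for increased lupus disease activity will cause the participant to be declared a treatment failure".
- NSAIDs (Protocol 7.7.1.5, repeated in SAP 15.6.15.7): "New NSAIDs may not be added after Day 1 unless given for <7 days".

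The SAP also takes Day 1 as the reference point. SAP 15.6.15.5 states "Dose of anti-malarial at baseline is the dose the subject received on the treatment start date (Day 1"), and SAP 15.6.15.7 states "Baseline is defined as the NSAID/Aspirin received on the treatment start date (Day 1").

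On review, SAP 15.6.15.3 states: "All potential TF rule violation are output programmatically and all adjudicated". SAP 7.1.1 requires a responder to be free of treatment failure at the current visit and every earlier one.

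**The concern.** Dating an unknown start to Day 1 is reasonable when the question is whether a drug belongs in the concomitant-medication tables. For deciding treatment failure it is the lenient choice: Day 1 is the last date on which a start is not a violation. The default also applies exactly when the case report form does not mark the drug as prior use.

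Failure is permanent under the main (Hybrid) estimand, so a missed one carries through Weeks 52, 64 and 104. The flare endpoints inherit it as well, because SAP 7.7.5 counts treatment failure as an event. For NSAIDs, the dose imputed to Day 1 also becomes one of the two reference levels in the 8-week windows before the key visits, which can weaken that later rule.

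**Working it through.** **1. The plan's own figures (context only; the point depends on none of them).** Protocol 10.2 gives 70 and 140 participants, 10% and 35% response, two-sided 5%, and at least 98% power. A two-proportion calculation gives 98.9%, and exact enumeration of the likelihood ratio test gives 99.0%. The stated minimum detectable effect of 11% also reproduces: with 7/70 in Arm A, the smallest significant Arm B count by the likelihood ratio test is 29/140, a difference of 20.7% − 10.0% = 10.7 points.

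**2. Tracing the date rule.** Suppose first dose is 05-JUN-2018, the prior-use box is unticked and there is no end date before first dose. A 30-day NSAID course that truly begins on 20-JUN-2018 starts on Day 20 − 5 + 1 = 16 and should be a failure. The table shows what the rule does with different recorded starts.

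| Recorded start | Start used | After Day 1? |
|---|---|---|
| blank | 05-JUN-2018 | no, not flagged |
| JUN-2018 | 05-JUN-2018 | no, not flagged |
| SEP-2018 | 01-SEP-2018 | yes, flagged |
| 2019 | 01-JAN-2019 | yes, flagged |
| 2018 | not settled by the text | see below |

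The first two rows are the point. In the last row there is no month to compare. If that counts as no mismatch, the start becomes Day 1. If it counts as a mismatch, the start becomes 1 January 2018. The text does not choose between them.

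**3. Looking for another catch.**

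- NSAIDs or aspirin taken as needed are reviewed whatever the start date (SAP 15.6.15.7).
- In Arms A and B, every immunosuppressant after Week 4 is clinically reviewed (SAP 15.6.15.6). Only a new agent stopped by Week 4 could slip through.
- Steroid increases close to withdrawal have their own review (SAP 15.6.15.4).
- SAP 15.6.15 has no rule for restricted drugs with a missing start date.
- SAP 5.3 counts a medication started on Day 1 as on treatment, not baseline. This conflicts with SAP 15.6.15.5 and 15.6.15.7 but does not close the gap, because a Day 1 start is still not after Day 1.

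The remaining exposure in Arms A and B is therefore anti-malarials and NSAIDs not taken as needed. Arm C adds immunosuppressants.

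**4. Size.** One case changes the endpoint only if the participant also has a blinded-assessor SLEDAI-2K of 2 or less, no other failure and no withdrawal. The most it can add is 1/70 = 1.43 points (Arm A) or 1/140 = 0.71 points (Arm B).

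To see when one case could matter, take the unadjusted likelihood ratio statistic G = 2 Σ O ln(O/E) with 7/70 in Arm A:

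- 28/140: expected responders 11.67 and 23.33, expected non-responders 58.33 and 116.67; G = 3.61, p = 0.057.
- 29/140: expected responders 12 and 24, expected non-responders 58 and 116; G = 4.07, p = 0.044.

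One Arm B participant moves this test across 0.05. Fisher's exact test gives 0.078 and 0.055 for the same tables and does not cross. At the planned rates Arm B would have 0.35 × 140 = 49 responders. With Arm A held at 7, losing significance by the likelihood ratio test would take 49 − 28 = 21 reclassifications.

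**The case against.** The strongest reply is that the gap is small and partly covered. Protocol 7.7 requires start and end dates for every medication, and medications are reviewed at each visit, so blank dates for on-study starts should be uncommon. The sentence in SAP 15.6.15.3 does not say that nothing else may be adjudicated: SAP 15.6.15.8 brings events found by monitoring into failure review, and blinded review precedes database lock. Arms A and B are mutually blinded and follow the same date rule, so no differential error is shown. Two supportive analyses are unaffected in the A versus B comparison through NSAIDs and anti-malarials: the treatment-policy estimand (SAP 7.1.4), which ignores treatment failure, and the analysis in SAP 7.10, which considers only current immunosuppressants and corticosteroids.

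All of this limits the size, and it stands. None of it is a specified check on missing start dates. Where the SAP foresaw that its program might miss a failure, it wrote an explicit catch; here it did not. The supportive analyses estimate something else and do not correct the main estimand.

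A reader might also infer that NSAIDs have no second route to review. The documents do not support that, because as-needed use is reviewed whatever its start date.

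**Conclusion.** The gap is real but narrow. For a fully missing start date, or a partial date in the month and year of first dose, with prior use unticked and no end date before first dose, the written rules do not flag a true on-study start. The participant can then be counted as a responder if all other criteria are met. The shift is at most 1.4 points per case in Arm A and 0.7 in Arm B, on target arm sizes. A few cases could matter near the significance boundary but not at the planned 10% versus 35%.

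Three stronger readings go beyond the documents:

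- **That every missed record adds a responder.** Many such participants would fail on another criterion, so the per-case figures are maxima. The number of records is not given and may be zero.
- **That a year-only date is certainly moved to Day 1.** On one reading a start as late as 31-DEC-2018 (Day 210 in the example) would be, but the wording is ambiguous and the conclusion does not rest on it.
- **That the rule favours the combination arm.** The direction of any bias between the blinded arms is unknown.

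The conclusion assumes that the program applies the date rule as written and that no unstated data query resolves these records first.

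**What to change.** In SAP 15.6.15.3 and 15.7.2.1, for the treatment-failure derivation only:

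1. Output to blinded adjudication, as a potential failure, every anti-malarial, NSAID and immunosuppressant record whose start was imputed to Day 1 and which is not marked as taken before the study. Do not re-date it automatically.
2. State how a year-only date is compared with the first-dose date, so that such records are either listed or deliberately excluded.
3. Reconcile SAP 5.3 with SAP 15.6.15.5 and 15.6.15.7 on whether a Day 1 start is baseline use.

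Keep the Day 1 imputation for descriptive tables. Moving all undated starts to Day 2 would be too broad. It does nothing for the aspirin rule or the steroid rule after Week 26, and it would remove the Day 1 reference dose from long-standing drugs whose prior-use box was left unticked.

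The cost is a few sentences and a short extra adjudication listing, which will include some of those long-standing drugs.

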15.8. Appendix 8: Laboratory Parameters and Toxicity Grades

| Laboratory Assessments | Parameters | | | |
|---------------------------------|---|---|--|--|
| Hematology | Platelet Count | RBC Indices: MCV MCH MPV MCHC %Reticulocytes | | WBC count with Differential: Neutrophils Lymphocytes Monocytes Eosinophils Basophils |
| | RBC Count | | | |
| | RDW | | | |
| | Hemoglobin | | | |
| | Hematocrit | | | |
| | Activated partial thromoplastin time | | | |
| | Prothrombin Time | | | |
| Clinical Chemistry ¹ | BUN | Potassium | Aspartate Aminotransferase (AST)/ Serum Glutamic-Oxaloacetic Transaminase (SGOT) | Total and direct bilirubin |
| | Creatinine | Sodium | Alanine Aminotransferase (ALT)/ Serum Glutamic-Pyruvic Transaminase (SGPT) | Total Protein |
| | Glucose – Nonfasting | Calcium (corrected) | Alkaline phosphatase | eGRF |
| Routine Urinalysis | 
 • Standard Urinalysis Macro and Urinalysis Micro (microscopic examination if blood or protein is abnormal) • Specific gravity • pH, Glucose, Protein, Blood, Ketones, Occult Blood, Bilirubin, Nitrite, Leukocyte Esterase by dipstick • Spot Urine (protein:creatinine ratio) | | | |
| Immunoglobulins | 
 • Serum isotypes: IgG, IgM, IgA | | | |
| Autoantibodies | 
 • ANA titer • Anti-dsDNA • aCL • Beta-2-glycoprotein • Lupus anticoagulant • Extractable nuclear antigens (ENAs) | | | |

| Laboratory Assessments | Parameters |
|--------------------------|--|
| Serum Complement | 
 • Complement C3 • Complement C4 |
| Urine Drug Screen | 
 • Amphetamines, Barbiturates, Benzodiazepines, Cocaine Metabolites, Marijuana Metabolites, Methadone, Opiates, Phencyclidine, Propoxyphene, Ethanol |
| Genetics | 
 • Blood sample collection |
| Belimumab PK | 
 • Blood sample collection |
| Rituximab PK | 
 • Blood sample collection |
| RNA Interferon Signature | 
 • Blood sample collection |
| PBMC | 
 • Blood sample collection |
| Immunogenicity | 
 • Blood sample collection |
| B Cell Subset | 
 • Blood sample collection |
| B-Cell Receptor | 
 • Blood sample collection |
| BLyS Protein | 
 • Blood sample collection |
| Other Screening Tests | 
 • Follicle-stimulating hormone and estradiol (as needed in women of non-childbearing potential only) • Serum human chorionic gonadotropin (hCG) pregnancy test (as needed for women of childbearing potential) • Serology (HIV antibody, hepatitis B surface antigen [HBsAg], and hepatitis C virus antibody) • |

NOTES :

1. Details of liver chemistry stopping criteria and required actions and follow-up assessments after liver stopping or monitoring event are stated in the protocol. All events of ALT $\geq 3 \times$ upper limit of normal (ULN) and bilirubin $\geq 2 \times$ ULN (>35% direct bilirubin) or ALT $\geq 3 \times$ ULN and international normalized ratio (INR) >1.5, if INR measured, which may indicate severe liver injury (possible Hy's Law), must be reported as an SAE (excluding studies of hepatic impairment or cirrhosis).

Laboratory parameters may need to have units converted for reporting. Equivalent units are:

$$1 \times 10^9 / \text{L} = 1,000,000,000 \text{ cells/L} = 1,000 \text{ cells}/\mu\text{L} = 1,000 \text{ cells}/\text{mm}^3$$

$$1 \text{ g/L} = 100 \text{ mg/dL} = 100 \text{ mg}/100 \text{ mL} = 1 \text{ mg/mL}$$

